7.2 Visit-Specific Procedures

7.2.1 Visit 1 (Screening; Days -31 to 0)

Written informed consent must be obtained prior to any study-related procedures. Potential subjects will be screened within 31 days prior to Visit 2 (Baseline) to assess their eligibility to enter the study. Only eligible subjects with axillary hyperhidrosis will be enrolled.

After informed consent is obtained, the following procedures will be performed:

- Collect and review subject medical history and demographics.
- Assess inclusion/exclusion criteria.
- Perform physical exam including collection of height and weight (see Section 8.1.1).
- Collect vital signs (blood pressure, heart rate, respiratory rate, and temperature) after subject has been seated for ≥2 minutes (see Section 8.1.5).
- Subject to complete the HDSM-Ax assessment.
 - Six multi-part questions and PGI-S question to be completed by the subject prior to other assessments.
 - Refer to Appendix 1 (HDSM-Ax).
- Review the subject's health (AEs).
- Perform UPT if applicable (FOCBP only). If positive, the subject shall be screen failed.
- Collect samples for laboratory assessments (hematology, chemistry and urinalysis) (see Section 8.1.6).
- Review concomitant medications/treatments and assess for washouts.
- Schedule the subject to return for Visit 2 (Day 1; Baseline) after any washout has been completed; must be within 31 days of Visit 1 (Screening).

7.2.2 Visit 2: Baseline (Day 1)

Any washouts required for prohibited medications (See Section 4.3) must be completed prior to Visit 2 (Baseline).

The following activities will be conducted:

- Provided the subject has passed all I/E criteria, randomize the subject according to separate instruction. Note the subject's randomization number and the IP concentration the subject is assigned (5% or 15% sofpironium bromide gel).
- Collect vital signs (blood pressure, heart rate, respiratory rate, and temperature) after subject has been seated for ≥2 minutes.
- Subject to complete the Hyperhidrosis Disease Severity Measure-Axillary assessment.

- Subject to complete Patient Global Impression of Severity (PGI-S) at the end of the HDSM-Ax questionnaire.
- Subject to complete the DLQI questionnaire.
 - \circ 10 questions to be completed by the subject.
 - Refer to Appendix 2.
- Subject to complete the HidroQoL questionnaire.
 - Only the first 100 subjects enrolled in the study to complete the questionnaire.
 - 18 questions to be completed by the subject.
 - Refer to Appendix 3.
- Perform local tolerability assessments (see Section 8.1.3).
- Review changes to the subject's health (AEs).
- Perform Urine Pregnancy Testing (UPT) if applicable (FOCBP only). If positive, the subject shall be excluded from the study.
- Pull from inventory, a pump container of correct IP concentration recalling the earlier randomization step. Record the unique IP gel pump container number on the source document and in the appropriate electronic data capture (EDC) (or IRT) data field. Dispense study product container 1 to the subject as follows:
 - Write patient number and initials on the study product container label.
 - Prime the pump (5 actuations) and discard expressed gel.
 - Weigh the primed pump and record in source prior to dispensing to the subject. Dispense the pump to the subject in the kit carton with the included 2 applicators
 - Provide subject with patient study drug application brochure, access to a study product application video and digital mobile application.
 - Review with subject the study drug application procedure (Refer to Appendix 5).
 - Instruct subject to apply the first application of study medication at home the evening of Visit 2 (Baseline).
- Review concomitant medications/treatments.
- Schedule the subject to return for the next study visit.

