11.1.3 Method for Assignment to Study Product Groups

All subjects who have signed an ICF will receive a 7-digit subject screening number, this number will be composed of a 1-digit study number (3), a 3-digit site number followed by a 3-digit sequentially assigned number stating at 001, at each site. For instance, the first subject from site 01 will have 3001001 as their assigned subject screening number; the subsequent subject from this site will have 3001002 as their assigned subject screening number. The first subject from site 02 will have 3002001 as their assigned subject screening number; the subsequent subject from this site will have 3002001 as their assigned subject screening number; the subsequent subject from this site will have 3002002 as their assigned subject screening number. This number will be unique to each subject and will be used to identify the subject throughout the study.

After subjects qualify for the study (as determined by the Investigator at the Screening Visit), they will be scheduled to return for a Baseline Visit where they will be randomized to one of the two investigational product concentrations (5% or 15%), notified of the IP gel concentration they are assigned to, and their screening number becomes their post-randomization subject number. Each kit carton will contain a treatment plastic pump, which will be labeled with the IP drug concentration contained within and have a unique bottle number displayed on the label. A kit of the proper drug concentration will be selected from inventory and dispensed to the subject after the proper prep/priming operation (see Section 5.2).

The next eligible subject will be assigned the next available randomization slot from the randomization list queue. In this manner, eligible subjects will be randomized to the investigational product in accordance with the randomization schedule. The Investigator will document the randomization and kit numbers dispensed to the subject in the source, in the IRT system and on the CRF. The tear-off portion of the carton label from the outer carton will be removed along the label perforation and placed into the study subject source file. In the event a subject is randomized but is not dispensed study medication (e.g., deemed ineligible at Baseline, withdraws consent) the randomization number will not be reassigned; the subject will be considered an early termination and the kit shall be placed in quarantine in the site's inventory.

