4. ANALYSIS POPULATIONS

Identification of the subjects to be included in each analysis population will be determined and finalized prior to database lock. Subjects will be classified into the Safety, Intent-to-Treat (ITT), Per Protocol (PP), and HidroQoL (HQL) populations according to the following definitions:

Safety Population

The Safety Population will include all subjects randomized in the study who received study drug at least once. Subjects will be included in the treatment group based on the majority of actual treatment they received (even if not the treatment group to which they were randomized).

ITT Population

The ITT Population will include all subjects who were randomized. Subjects will be included in the treatment group to which they were randomized, regardless of the treatment received.

PP Population

The PP Population will be a subset of the ITT Population and will include subjects who meet the following criteria:

- Meets the inclusion/exclusion criteria
- Has not taken or applied any interfering concomitant medications.
- Completed the following visits:
 - o Visit 1 (Screening) and the required HDSM-Ax data collection
 - o Visit 2 (Baseline) and the required HDSM-Ax data collection
 - o Visit 4 (Week 4), and the required HDSM-Ax data collection
 - o Visit 7 (Week 12), and the required HDSM-Ax data collection
 - o Visit 10 (Week 24), and the required HDSM-Ax data collection
 - o Visit 16 (Week 48), and the required HDSM-Ax data collection
 - o Visit 17 (Week 52), and the required HDSM-Ax data collection
- Treatment received per randomization assignment

HOL Population

The HQL Population will be used for HidroQol analyses. Subjects with "Yes" noted for the question "Subject flagged for the Baseline-Visit 5 HidroQol Protocol" on the Subject CRF page are included. The first 100 subjects \geq 17 years of age enrolled were eligible for this population.

Version: 1.0 Page 17 of 51

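### Protocol 7.2.2 lists randomisation and the assigned concentration before the Visit 2 eligibility checks and subjective baseline scores, against its own proviso

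*Protocol*

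**What the plan says.** Protocol 7.2.2 begins the Visit 2 activities with "Provided the subject has passed all I/E criteria, randomize the subject according to separate instruction" and continues in the same bullet: "Note the subject's randomization number and the IP concentration the subject is assigned (5% or 15% sofpironium bromide gel". Below it come vital signs, HDSM-Ax, PGI-S, DLQI, HidroQoL (first 100 subjects), local tolerability, adverse events and the UPT. On the UPT it says "If positive, the subject shall be excluded from the study". The dispensing bullet follows: "Pull from inventory, a pump container of correct IP concentration recalling the earlier randomization step".

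Protocol 11.1.3 has the Investigator determine at Screening that a subject qualifies. The subject then returns for Baseline, is randomised, and is "notified of the IP gel concentration they are assigned to". It also provides for what happens next: "In the event a subject is randomized but is not dispensed study medication (e.g., deemed ineligible at Baseline, withdraws consent". Such a subject keeps the randomisation number and counts as an early termination.

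Two eligibility criteria depend on Visit 2 results. Inclusion 2a (Protocol 4.2) needs an HDSM-Ax of 3 to 4 at Visit 2 as well as at Screening. Exclusion 12 (Protocol 4.3) rules out pregnancy.

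The SAP takes Visit 2 as baseline for HDSM-Ax (8.1.4) and for local tolerability (9.5). On the analysis set, SAP 4 says "The ITT Population will include all subjects who were randomized". Protocol 10.1 also required that study drug had been dispensed; SAP 13 declares the change.

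**The concern.** Both arms are open-label, so the baseline visit is the one point at which subject and Investigator can score without knowing the concentration. If the listed order is followed, that protection is lost. An HDSM-Ax, DLQI, HidroQoL, burning or itching score given after learning of 5% or 15% may differ by arm for reasons unrelated to disease, and so may the Investigator's dryness, scaling and erythema scores. Local tolerability is a primary endpoint, and every post-baseline shift table is read against this value.

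The second issue is eligibility. A site that randomises on arrival cannot yet know the Visit 2 HDSM-Ax or UPT result, so it may randomise subjects who then fail. Under the SAP definition those subjects belong to the ITT set.

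**Working it through.** The plan gives no figure to reproduce. SAP 2.6 states that no formal sample size calculation was made, and neither document gives an SD or an expected change. The check is mainly of text; the arithmetic below only illustrates scale.

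**1. Order against proviso.** The randomisation bullet requires all criteria to be passed. Two of them rest on the HDSM-Ax and UPT listed below it. Carried out as listed, the condition cannot be met; if the condition is honoured, the listed order cannot be the order of work. The two must be reconciled.

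**2. Which scores does the proviso protect?**

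| Visit 2 score | Needed for eligibility? | Collected before Visit 2? |
|---|---|---|
| HDSM-Ax | Yes (2a) | Yes, Screening |
| PGI-S | No, but it is question 6 of the HDSM-Ax form | Yes, Screening |
| DLQI | No | No |
| HidroQoL | No | No |
| Local tolerability | No threshold | No |

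Honouring the proviso puts HDSM-Ax, PGI-S and the UPT ahead of randomisation. It does nothing for the last three rows, which have no earlier score to fall back on (Protocol 7.1). Protocol 8.1.7 only places self-assessments before Investigator assessments; it does not place either before randomisation.

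**3. How a baseline shift carries through.** Improvement = baseline − Week 48. If knowledge of the arm raises the reported baseline by s and leaves Week 48 unchanged, mean improvement in that arm rises by s. The protocol synopsis averaged Screening and Day 0, under which a Visit 2 shift would count as s/2. SAP 13 replaces this with Day 1 alone, so it counts in full.

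Responder rate under a normal approximation: Φ((μ + s − c)/σ), with c the threshold. Assumed, not from the documents: μ = 1.5, σ = 1.0, and s as shown.

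| s | ≥1 point | ≥1.5 points | ≥2 points |
|---|---|---|---|
| 0 | 69.1% | 50.0% | 30.9% |
| 0.10 | 72.6% | 54.0% | 34.5% |
| 0.25 | 77.3% | 59.9% | 40.1% |
| 0.50 | 84.1% | 69.1% | 50.0% |

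For example, s = 0.25 and c = 1 gives Φ(0.75) = 77.3%, against Φ(0.50) = 69.1%.

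**4. Ineligible subjects in the SAP ITT set.** Let e be the share of 300 randomised who are found ineligible afterwards (assumed 1%, 2%, 5%, 10%: 3, 6, 15, 30 subjects), and p = 60% the assumed true responder rate.
- No Week 48 record: SAP 3.1 uses subjects with available data as denominator and SAP 8.1.1 imputes nothing, so the rate stays 60%.
- A same-day early-termination assessment (Protocol 7.4 asks for the Visit 16 evaluations) counted as non-response: p(1 − e) = 59.4%, 58.8%, 57.0%, 54.0%.
- Baseline HDSM-Ax mean, if these subjects score 2.5 and the others 3.5 (assumed): e × (2.5 − 3.5) = −0.01, −0.02, −0.05, −0.10.

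**The case against.** The best reply is that the bullets are a checklist. The Screening list in Protocol 7.2.1 places the criteria assessment second, before the examinations and tests that decide it. It lists HDSM-Ax after the physical exam and vital signs while asking that it be done ahead of other assessments. In 7.2.2 itself, concomitant medication review, on which several exclusions depend, follows dispensing. The phrase "recalling the earlier randomization step" shows only that randomisation precedes dispensing. Section 11.1.3 does not say that subjects are notified before the questionnaires, and its ineligible-at-Baseline case is a contingency. This largely stands: the lists are not strictly chronological, and the documents do not clearly instruct sites to randomise first. But no text in either document puts DLQI, HidroQoL or tolerability before randomisation, and 11.1.3, with qualification at Screening and ineligibility discovered afterwards, lets a site follow the list literally.

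Exclusion 1 requires otherwise normal axillae, which leaves tolerability baselines limited room to move. In an open-label study later scores are also exposed to knowledge of the dose, so shifts at baseline and Week 48 could partly cancel. Both points stand, and are why no direction is claimed.

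The order may also be fixed elsewhere. Randomisation follows a separate instruction, IRT and eCOA manuals exist, and the SAP is based on protocol Amendment 4 whereas the protocol supplied is Amendment 01. This stands, and must be checked first.

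**Conclusion.** The contradiction in 7.2.2 is real, and the risk to subjective baselines follows if sites work down the list. DLQI, HidroQoL and local tolerability are unprotected on either reading; HDSM-Ax and PGI-S are exposed only if the list is followed literally. What could be biased is the descriptive by-arm output: change from baseline, responder proportions and tolerability shifts. Size and direction are unknown, and the percentages above rest wholly on assumed inputs.

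Three stronger inferences are not supported.
- **That every baseline value is affected.** Laboratory samples are taken at Screening and not at Visit 2, so the laboratory baseline normally predates randomisation. Medical history, height and weight are also from Screening, and knowledge of the concentration would not plausibly alter a UPT result.
- **That the ITT set is materially contaminated.** This arises only under the SAP definition. Such subjects would appear in disposition and ITT baseline tables, with nil to small effect on efficacy summaries. The Safety set, used for the primary endpoints, requires a dose, and the PP set requires the criteria to be met.
- **That a between-arm test is invalidated.** SAP 3.1 plans none.

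**What to change.** First check Amendment 4 and the separate randomisation instruction; if either already sets the order, only the wording needs aligning. Otherwise:

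- Reorder 7.2.2: HDSM-Ax with PGI-S, DLQI, HidroQoL, vital signs, local tolerability, adverse event and concomitant medication review, and UPT; then confirmation of all criteria; then IRT randomisation, disclosure of the concentration and dispensing.
- State in 11.1.3 that randomisation and disclosure occur only once the Visit 2 questionnaires, tolerability scores and UPT are complete and all criteria are confirmed.
- If subjects are already enrolled, compare IRT and eCOA timestamps and report, by arm, how many baseline scores followed randomisation.

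The cost is a change of wording and, for enrolled subjects, one timestamp comparison. Visits and procedures are unchanged.

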7.2.3 Visits 3-6 (Weeks 2, 4, 6, and 8) ±3 Days

Visits 3, 4, 5 and 6 will occur as separate visits on Weeks 2, 4, 6, and 8 respectively, after the Baseline visit (Visit 2).

No more than 14±3 days may elapse between Visit 2 (Baseline) and Visit 3 (Week 2).

The following activities will be conducted:

- Collect vital signs (blood pressure, heart rate, respiratory rate and temperature) after subject has been seated for ≥2 minutes.
- Subject to complete HDSM-Ax assessment.
 - Subject to complete PGI-S at the end of the HDSM-Ax questionnaire.
- Subject to complete the DLQI questionnaire at Visit 3 (Week 2) and Visit 5 (Week 6).
- Subject (only the first 100 subjects enrolled in the study) to complete HidroQoL at Visit 3 (Week 2) and Visit 5 (Week 6).
- Perform local tolerability assessments.
- Review changes to the subject's health (AEs).

- Perform UPT if applicable (FOCBP only) at Visit 4 (Week 4) and Visit 6 (Week 8). If positive, the subject shall be withdrawn from the study.
- Collect subject's previously dispensed study product container (1 of 12 at Visit 4 and 2 of 12 at Visit 6), weigh and record weight of container.
- Dispense study product container (2 of 12 at Visit 4; 3 of 12 at Visit 6) to the subject
 - Pull from inventory, a pump container of correct IP concentration recalling the randomization step (and which should match with the subject's returned product container). Record the unique IP gel pump container number on the source document and in the appropriate EDC (or IRT) data field.
 - Write patient number and initials on the study product container label.
 - Prime the pump (5 actuations) and discard expressed gel.
 - Weigh the primed pump and record in source prior to dispensing to the subject.
- Evaluate subject compliance:
 - Ask subjects if they applied the study product to the right and left axilla each evening as directed and confirm reason for any missed doses.
 - Verbally confirm application process.
- Collect samples for laboratory assessments (hematology, chemistry, and urinalysis) at Visit 5 (Week 6) only.
- Review concomitant medications/treatments.
- Remind subject to bring their study medication product container to next visit.
- Schedule the subject to return for the next study visit.

- Remind subject to bring their study medication to next visit.
- Schedule the subject to return for the next study visit.

7.2.5 *Visit 17 (End of Study)* ±5 *Days*

The following activities will be conducted:

- Perform physical exam including collection of height and weight.
- Collect vital signs (blood pressure, heart rate, respiratory rate and temperature) after subject has been seated for ≥2 minutes.
- Subject to complete HDSM-Ax assessment.
 - Subject to complete PGI-S at the end of the HDSM-Ax questionnaire.
- Perform local tolerability assessments.
- Review changes to the subject's health (AEs).
- Only if the subject did not return the study product container 12 at Visit 16, then weigh and record weight of container.
- Review concomitant medications/treatments.
- Discharge subject from the study.

7.3 **Unscheduled Visits**

If a subject is seen for an unscheduled visit, an assessment and record of AEs should be completed, as appropriate. Additional evaluations should be performed as necessary, and the appropriate CRF pages should be completed.

7.4 **Early Discontinuation of Subjects**

It is the right and duty of the Investigator to discontinue a subject's participation if the subject's health or wellbeing is threatened by continuation in the study. In the event of premature discontinuation, the Investigator should determine the primary reason for discontinuation. A subject may be discontinued from the study if any of the following circumstances occur:

- The subject experiences a serious adverse event (SAE) rendering him or her unable to continue study participation.
- The subject experiences an AE that in the opinion of the Investigator may pose a significant risk for continued participation of the subject in the study.

- The subject is unable to physically or mentally tolerate the use of the investigational product.
- An exclusion criterion becomes apparent at any time during the study; the Medical Monitor must be contacted to discuss prior to discontinuing subject participation.
- The subject is not compliant with the study procedures; the Medical Monitor must be contacted to discuss prior to discontinuing subject participation.
- The subject voluntarily withdraws from the study. When possible, identify the reason the subject withdrew consent should be documented with particular attention paid to whether an underlying AE is at cause.
- If for any reason per the Investigator's or the Sponsor's judgment, discontinuation is in the subject's best interest.
- If the subject becomes pregnant.

Subjects who discontinue the study prior to the completion of all treatment visits will be asked to complete the evaluations corresponding to Visit 16 (Week 48, End of Treatment). The Sponsor will be notified of early discontinuation as soon as possible during the study.

8 RESPONSE MEASURES AND SUMMARY OF DATA COLLECTION METHODS

8.1 Safety Measures

The following safety assessment measures will be conducted as indicated in Section 7.1, Time and Events Table.

- Adverse events
- Local tolerability assessments including burning, itching, dryness, scaling and erythema
- Vital signs (blood pressure, pulse rate, respiratory rate, and temperature)
- Laboratory tests (hematology, chemistry, and urinalysis) and pregnancy testing in FOCBP

8.1.1 *Physical Exam*

Physical examination will include assessments of the head, eyes, ears, nose, throat, skin, thyroid, neurological, lungs, cardiovascular, abdomen (liver and spleen), lymph nodes and extremities. Height and weight will also be measured and recorded.

8.1.2 Adverse Events

Adverse events (AEs; See Section 9.2) will be collected for all untoward medical occurrences in a subject entered into this clinical study (e.g., signed consent), whether or not a pharmaceutical product has been administered. Any event, including local tolerability assessments (see Section 8.1.3), that requires specific treatment, results in interruption of treatment, or results in discontinuation of the subject from the study will also be reported as an AE.

Care will be taken not to introduce bias when detecting AEs and/or SAEs. Open-ended and non-leading verbal questioning of the subject is the preferred method to inquire about AE occurrence.

Appropriate questions include:

- "How are you feeling?"
- "Have you had any (other) medical problems since your last visit/contact?"
- "Have you taken any new medicines, other than those provided in this study, since your last visit/contact?"

8.1.3 *Local Tolerability Assessments*

Local tolerability assessments (See Appendix 4) will be evaluated through assessment of selected local signs and symptoms at the drug-application site. Burning, itching, dryness, scaling and erythema will be assessed using standardized 5-point scales (0-Absent to 4-Severe). These assessments are to be performed for both axillae individually. Subject assessments (burning and itching) will be made prior to the Investigator assessments (dryness, scaling and erythema).

Subject Local Tolerability Assessments: Burning and itching for each axilla will be reviewed with the subject and assessed for the previous 24 hours using the standardized scales.

Investigator Local Tolerability Assessments: Dryness, scaling, and erythema for each axilla will be assessed by the Investigator using the standardized scales.

Local tolerability signs and symptoms that result in the subject's requiring a concomitant therapy, interruption of treatment, or discontinuation from the study, will be reported as an AE.

8.1.4 *Recommendations for Dose Interruption*

To manage AEs, the Investigator may consider interruption of treatment, and/or the use of concomitant therapy. Recommended concomitant therapy includes topically applied corticosteroids. Recommendations for dose interruption are described in the table below:

Recommended Dose Interruption

Dose Interruption		
First Dose InterruptionHold treatment until the adverse event has resolved. Result dosing.		
Second Dose Interruption	Hold treatment until the adverse event has resolved. Decrease dosing to every other day.	

Subjects who do not respond to a dose interruption or concomitant therapy can have the study drug withdrawn and be discontinued from the study.

8.1.5 *Vital Signs*

Subjects should be seated for ≥ 2 minutes prior to measurements. Pulse rate (bpm) will be counted over 60 seconds. Blood pressure (mmHg) will be measured with a sphygmomanometer.

Vital sign measurements will include systolic and diastolic blood pressure, pulse rate, respiratory rate, and temperature.

8.1.6 *Clinical Laboratory Assessments*

Hematology, clinical chemistry, urinalysis and additional parameters to be tested are listed below:

Hematology

Platelet Count	RBC Indices :	Automated WBC Differential:
RBC Count	MCV	Neutrophils
WBC Count (absolute)	МСН	Lymphocytes
Reticulocyte Count	МСНС	Monocytes
Hemoglobin		Eosinophils
Hematocrit		Basophils

Clinical Chemistry

BUN	Chloride	Alkaline phosphatase
Creatinine	AST (SGOT)	Total and direct bilirubin
Sodium	ALT (SGPT)	
Potassium	GGT	

Routine Urinalysis

Specific gravity
pH, glucose, protein, blood and ketones by dipstick
Microscopic examination (if blood or protein is abnormal)

Other Screening Tests

Urine Pregnancy Test (females of childbearing potential* only, using UPT tests provided by the Sponsor.)

* Females of childbearing potential for this study includes any female capable of becoming pregnant who has not undergone successful surgical sterilization (hysterectomy, bilateral tubal ligation [≥6 months prior to baseline] or bilateral oophorectomy) or is not postmenopausal (defined as amenorrhea >12 consecutive months in women ≥55 years of age).

All results will be reported and must be reviewed by the Investigator or designee. Abnormal results shall be assessed for clinical significance. Repeat lab testing may be requested at the discretion of the Investigator. If an AE should require laboratory testing, the results of the test should be obtained by the investigative site and filed in the subject's documentation.

8.1.7 *Subject Assessments*

Subjects must complete ALL self-assessments while at the clinic (e.g., HDSM-Ax, DLQI, PCI-S, PCI-C, HidroQoL) prior to assessments being made by the Investigator. Please see Appendix 1, Appendix 2, and Appendix 3 for a full description of these assessments. The HDSM-Ax, DLQI, PCI-S, PCI-C, and HidroQoL assessments will be collected electronically using a tablet device. Site personnel will be trained and a separate eCOA manual will be supplied.

